
12 MEASUREMENT OF EFFECT

12.1 RESPONSE CRITERIA

12.1.1.1 Evaluable for toxicity

All patients who receive at least one dose of protocol therapy will be evaluable for toxicity from the time of their first treatment with TICE BCG or rV-PANVAC™. All observed toxicities will be tabulated using CTCAE v4.1 and a previously published, vaccinia toxicity grading scale used with this vaccine³³ by the highest grade experienced for each patient and presented for each study arm.

12.1.1.2 Evaluable for objective response

Only those patients who have biopsy-proven disease present at baseline, have received at least one cycle of therapy (6 or fewer weekly intravesical doses of BCG), and have had their disease re-evaluated will be considered evaluable for response. These patients will have their response classified according to the definitions stated below.

In order to compare the secondary outcomes between study arms, all durations will be measured from the start of TICE BCG therapy (week 3). This is the start of therapy for the TICE BCG arm alone. BCG is not started at week 0 for two reasons: 1) to allow adequate healing from previous TURBT and 2) allow vaccinia priming vaccine to be given to combination group at week 0 with enough recovery time to possibly make the administration of BCG in week 3 safer in these patients. Furthermore, by following this schema, patients in each group will start BCG at the same time after study entry.

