12.1.1.3 Recurrence-free survival

The recurrence-free survival duration will be measured from the start of TICE BCG therapy (week 3) until disease recurrence or death due to any cause in each arm. Recurrence is suspected and/or determined by urine cytology and/or cystoscopic exam and then confirmed pathologically after a TURBT. Positive cytology in the absence of pathologic confirmation is not considered to be a recurrence.

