Patient accrual is targeted at one patient per month during the first 6 months and 2 patients per month afterwards, and follow-up period after completing accrual will be 12 months. The power calculation was based on one-sided log-rank test at 15% significance level. Sample size, power and duration of the study are presented in the table below. With a total number of 49 patients, the power is 84% (see table below). Under this scenario, the expected number of events (recurrence or death) is 40. In order to allow for the possibility of a small number of unevaluable patients, the accrual ceiling will be set at 54 patients.

	Subgroup 1 1-year recurrence-free survival for BCG persistent patients who failed 1 BCG induction course	Subgroup 2 1-year recurrence-free survival for BCG persistent patients who failed 2 or more BCG induction courses	Subgroup 3 1-year recurrence-free survival for BCG naïve patients	Total sample size	Power (%)	Duration of accrual (months)	Expected number of events (recurrence or death)
Treatment benefit	HR=2.277 1-year RFS: BCG alone: 37.5% BCG+PANVAC: 65%	HR=2 1-year RFS: BCG alone: 20% BCG+PANVAC: 44.7%	HR=1.7 1-year RFS: BCG alone: 48% BCG+PANVAC: 65%	49	84	28	40

One interim analysis for futility will be performed according to the stopping procedure.³⁹ Specifically, the interim analysis will be performed when half of the expected events (20) have been observed. At that time, if the observed event rate of the TICE BCG+PANVAC arm is higher than that of the TICE BCG alone arm (i.e. the hazard ratio ≥ 1), we would consider terminating the trial and concluding that an advantage for the BCG+PANVAC regimen has not been established.

For the purpose of protecting patient safety, we implement the following stopping rule for safety monitoring of patients who receive the combination therapy.

If one patient experiences a grade 5 event, thought to be possibly or probably due to the combination therapy, the study will be stopped. For grade 3 or 4 event, the study will be stopped according to the following stopping rule. These adverse events are described in more detail in Section 7.

Number of patients	No. of grade 3 or 4 serious adverse events
3-9	3
10-18	4
19-26	5

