14.4.2 Evaluation of Response

All patients included in the study must be assessed for response to treatment, even if there are major protocol treatment deviations or if they are ineligible.

All of the patients who met the eligibility criteria (with the possible exception of those who received no study medication) should be included in the main analysis of the response rate.

All conclusions should be based on all eligible patients. Subanalyses may then be performed on the basis of a subset of patients, excluding those for whom major protocol deviations have been identified (e.g., early death due to other reasons, early discontinuation of treatment, major protocol deviations, etc.). However, these subanalyses may not serve as the basis for drawing conclusions concerning treatment efficacy, and the reasons for excluding patients from the analysis should be clearly reported. The 95% confidence intervals should also be provided.

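### The sections on who enters the primary recurrence-free survival comparison conflict, and none gives an intention-to-treat set or a start time for a randomised patient who never receives BCG

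*Combined protocol and SAP*

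**What the plan says.** Four places in the protocol bear on the primary analysis set.

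- **Section 12.1.1.2**, headed as evaluability for objective response, requires biopsy-proven disease at baseline and that patients "have received at least one cycle of therapy (6 or fewer weekly intravesical doses of BCG), and have had their disease re-evaluated". It then points to the definitions that follow. Those are RFS, progression-free survival and time to recurrence.
- **Section 12.1.1.3** gives RFS as "measured from the start of TICE BCG therapy (week 3) until disease recurrence or death due to any cause". Recurrence must be confirmed pathologically after a TURBT.
- **Section 14.4.2** says every patient must be assessed despite deviations or ineligibility. It puts all eligible patients in the main analysis, "with the possible exception of those who received no study medication", and rests conclusions on all eligible patients. Early death and early discontinuation appear as reasons for exclusion in subanalyses only, and those may not support efficacy conclusions. The text is written for a response rate, which is not an endpoint of this trial.
- **Section 14.1** sizes the trial on RFS: "The power calculation was based on one-sided log-rank test at 15% significance level". It adds: "In order to allow for the possibility of a small number of unevaluable patients, the accrual ceiling will be set at 54 patients". The term is not defined for RFS.

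The trial is open label (Précis). The combination arm is vaccinated in week 0; the control arm receives nothing until BCG in week 3 (Section 5.1).

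**The concern.** A randomised comparison is protected when every randomised patient is analysed in the assigned arm. Each set described here lets patients leave because of something that happens after randomisation: not starting treatment, not being re-evaluated, or being found ineligible. Patients and investigators know the assignment, so these events may depend on it.

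Three gaps follow.

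1. Two sections could be taken to govern RFS, and they treat early deaths in opposite ways. An analyst could follow either.
2. If Section 14.4.2 governs, its exception for untreated patients works differently by arm. A control patient who leaves before week 3 has had no study drug and may be dropped. A combination patient who leaves at the same time has been vaccinated and stays.
3. That combination patient stays in the set but has no RFS time, because the clock starts at BCG.

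At stake are the hazard ratio and the one-sided 15% error rate of a test with about 40 events, where a few patients matter.

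**Working it through.** **1. The plan's own figures.** Inputs from Section 14.1: RFS at 1 year of 37.5% v 65%, 20% v 44.7% and 48% v 65%; subgroup mix 1:5:1; 12 months of follow-up after accrual closes; and "Patient accrual is targeted at one patient per month during the first 6 months and 2 patients per month afterwards". Allocation is 1:1 (Section 4.3).

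- Hazard ratios, ln(control rate)/ln(combination rate): 2.277, 2.00 and 1.70, as stated.
- Accrual of 49: 6 + (49 − 6)/2 = 27.5 months (stated: 28).
- Subgroup sizes: 7, 35 and 7, so 3.5, 17.5 and 3.5 per arm.
- Event probability for a patient with F months of follow-up: 1 − p^(F/12), where p is the 1-year RFS. Averaged over entry times (control, combination): 0.839, 0.569; 0.942, 0.782; 0.752, 0.569.
- Expected events: 3.5 × (0.839 + 0.569) + 17.5 × (0.942 + 0.782) + 3.5 × (0.752 + 0.569) = 4.9 + 30.2 + 4.6 = 39.7 (stated: 40).
- Power by Freedman's formula at the average hazard ratio of 1.99: Φ[√40 × 0.99/2.99 − 1.036] = Φ(1.058) = 85.5%. Simulated log-rank tests (4,000 runs) give 85.3% stratified and 85.0% unstratified. Stated: 84%.

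The plan's figures reproduce. They assume follow-up to the end of the study, as the stated 40 events require. Capping follow-up at 12 months per patient would give about 30 events and 79% power, which is a separate matter from the analysis set.

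**2. The sections side by side.**

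| Randomised patient | Evaluable under 12.1.1.2 | In main set under 14.4.2 | RFS time under 12.1.1.3 |
|---|---|---|---|
| Control, leaves before week 3 | No | May be dropped | None |
| Combination, vaccinated, leaves before BCG | No | Yes, if eligible | None |
| Either arm, starts BCG, dies before re-evaluation | No | Yes, if eligible | Event at death |
| Either arm, treated, later found ineligible | Yes, if re-evaluated | No | Defined |

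No row gets the same treatment in all three columns.

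**3. The week-3 origin.** The log-rank statistic depends only on the order of the times. Adding the same constant to every event and censoring time leaves it unchanged. The planned gap is three weeks in both arms (taking week 0 as randomisation), so the gap alone does not bias the test. Bias needs losses or BCG delays before the clock starts that differ by arm.

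**4. Effect of the set on power.** Analysing all 54 gives 44.3 expected events and 88–89% power by simulation. Dropping 5 of 54 (9.3%) at random leaves 40.3 events, 86% power and a simulated type I error of 0.16, within simulation noise of 0.15.

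**5. An illustration, not an estimate.** This shows how sensitive the test is to outcome-dependent exclusions. Null trials of 54 were simulated with the earliest failures deleted from one arm only.

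| Deleted | Error, combination arm only | Error, BCG arm only |
|---|---|---|
| 1 | 0.20 | 0.12 |
| 3 | 0.29 | 0.08 |
| 5 | 0.37 | 0.05 |

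Under the planned effect, the BCG-arm deletions lower power from 0.89 to 0.87, 0.78 and 0.70.

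**The case against.** The strongest reply is that Section 12.1.1.2 is headed for objective response and nowhere says that it defines the RFS set, while the statistical section says nearly the reverse. A reader might infer that the plan discards early deaths. The documents do not establish that: it is one reading of conflicting text, and Section 14.4.2 points away from it. What stands is that Section 12 defines no response category, so the pointer in 12.1.1.2 leads only to the time-to-event endpoints. Section 14.4.2 in turn is written for a response rate.

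A reader might also infer that the week-3 clock itself biases the comparison. It does not. Section 12.1.1.2 gives a reason for it, and the planned shift is common to both arms. The missing start time for patients without BCG stands.

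The imbalance between arms arises only under Section 14.4.2, and there the exclusion is a possibility, not a rule. Section 12.1.1.2 requires BCG in both arms.

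The error rates in step 5 must not be taken as a bound. A recurrence confirmed after TURBT has by definition been re-evaluated. Among patients who start BCG, the re-evaluation condition can therefore remove only deaths as events, not the earliest recurrences. Step 5 also puts the whole trial's allowance of five in one arm. And a single grade 5 event possibly due to the combination stops the study (Section 5.4.2), which limits such deaths, though not deaths from other causes.

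Last, Section 11 already keeps patients followed elsewhere on study and obtains their outside pathology, so much of the needed follow-up is planned.

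**Conclusion.** The concern holds as a conflict and an omission. The plan describes more than one set, none is intention-to-treat, and RFS has no time origin for a randomised patient who never starts BCG. This takes the RFS definition in Section 12.1.1.3 as the primary endpoint, since Section 14.1 tests RFS and defines it nowhere else.

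The size and direction of any bias are unknown. They depend on early losses and BCG delays by arm, which the documents do not give. Exclusions unrelated to outcome would not bias the test and would cost little power; those related to outcome could move the error rate either way. A firmer claim, that the plan deletes deaths or inflates the error to a stated figure, is not supported. Severity: should-fix.

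**What to change.** In Sections 14.1 and 14.4.2, state one primary set and one clock:

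- The primary RFS log-rank test includes all randomised patients in their assigned arm, whatever their eligibility, treatment received or re-evaluation status.
- Time runs from randomisation to pathologically confirmed recurrence or death from any cause.
- A death before re-evaluation is an event on the date of death.
- Living patients without recurrence are censored at the last disease assessment, or at randomisation if there is none.

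Limit the Section 12.1.1.2 conditions and the week-3 origin to labelled sensitivity analyses. Replace the undefined reference to unevaluable patients in Section 14.1 with an allowance for patients lost without an assessment.

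The cost is wording. The sample size need not change. A living patient never assessed still adds nothing to the test, but is now reported; the gain is in deaths and in patients who stop early and are assessed later. RFS times lengthen by about three weeks in both arms, which slightly raises 12-month estimates. If no event is recorded in those weeks and planning rates hold in the largest subgroup, 20% becomes 0.20^(49/52) = 21.9% and 44.7% becomes 0.447^(49/52) = 46.8%.

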12.1.1.3 Recurrence-free survival

The recurrence-free survival duration will be measured from the start of TICE BCG therapy (week 3) until disease recurrence or death due to any cause in each arm. Recurrence is suspected and/or determined by urine cytology and/or cystoscopic exam and then confirmed pathologically after a TURBT. Positive cytology in the absence of pathologic confirmation is not considered to be a recurrence.

12.1.1.4 Progression-Free Survival

PFS is defined as the duration of time from start of treatment to time of progression or death, whichever occurs first. The duration of progression-free survival is measured from the start of TICE BCG therapy (week 3) until progression or death due to any cause in each study arm. Progression is defined as upstaging from a lower stage to a higher stage (e.g., Ta to T1 or T1 to T2-4; or any N+ or M+ in these high grade tumors).

12.1.1.5 Time to Tumor Recurrence

The duration of time measured from the start of TICE BCG therapy (week 3) until recurrence is noted.

13 DATA COLLECTION AND REPORTING/REGULATORY REQUIREMENTS

13.1 DATA COLLECTION

An enrollment log will be maintained in the regulatory binder/file which is the only location of personal identifiers with unique subject identification number.

All data will be stored by a patient code identification number only, without personal identifiers, and linked to samples by that identification number in Labmatrix. Clinical Data will be entered into the NCI C3D database. Data will be collected using protocol-specific case report forms, and verified for accuracy and completeness. Data should be entered into the data base in a timely manner. Hard copies of data will be stored in locked secured areas and data will be entered onto a secured electronic data base. The following protocol-specific study forms will be complete and stored: eligibility checklist (developed by Central Registration Office, CRO). A copy of all serious AE forms will be kept in the research record.

Data will be verified to ensure that:

- Eligible patients are confirmed and eligibility checklist was completed. Consent form must be signed prior to registration with Central Registration.
- Treatment is given according to protocol (dated notes about doses given, complications, and clinical outcomes).
- Toxicity is assessed according to protocol (laboratory report slips, etc.)
- Response is assessed according to protocol (X-ray, scan, lab reports, and date noted on clinical assessment, as appropriate).
- Drug Accountability Records are kept for each patient.

All data obtained during the conduct of the protocol will be kept in secure network drives or in approved alternative sites that comply with NIH security standards. Primary and final analyzed data will have identifiers so that research data can be attributed to an individual human subject participant.

All adverse events, including clinically significant abnormal findings on laboratory evaluations, regardless of severity, will be followed until return to baseline or stabilization of event. Patients will be followed for adverse events for 30 days after removal from study treatment or until off-study, whichever comes first.

An abnormal laboratory value will be considered an AE if the laboratory abnormality is characterized by any of the following:

- Results in discontinuation from the study
- Is associated with clinical signs or symptoms
- Requires treatment or any other therapeutic intervention
- Is associated with death or another serious adverse event, including hospitalization.

- Is judged by the Investigator to be of significant clinical impact
- If any abnormal laboratory result is considered clinically significant, the investigator will provide details about the action taken with respect to the test drug and about the patient's outcome.

End of study procedures: Data will be stored according to HHS, FDA regulations, and NIH Intramural Records Retention Schedule as applicable.

Loss or destruction of data: Should we become aware that a major breach in our plan to protect subject confidentiality and trial data has occurred, this will be reported expeditiously per requirements in section [7.2.1](#) .

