5 TREATMENT PLAN

5.1 STUDY DESIGN

This is a phase II study in subjects with non-muscle invasive (stages Ta, T1, and/or CIS) high grade urothelial carcinoma of the bladder who have failed at least one course of intravesical BCG. The study will be halted for 28 days after the first six patients with combination therapy are accrued and successfully treated. If any Grade 3 or greater toxicities are observed that do not resolve with conservative management, then they will be discussed with CTEP. With preliminary evidence of safety, the remaining subjects will be accrued to the trial. (See **SCHEMA**)

- 5.1.1 All subjects will receive BCG (TICE strain, 50 mg) intravesically as per usual standard of care once weekly (+/- 2 days) starting in week 3 for a total of 6 weeks (last dose in week 8).
- 5.1.2 Subjects in the combination arm will receive the pox viral vaccines that contain the transgenes for CEA and MUC-1 (both with modified HLA-A2 agonist epitopes) as well as 3 human T-cell costimulatory molecules, B7-1, ICAM-1, and LFA-3 [rV-PANVAC™ (vaccinia) and rF-PANVAC™ (fowlpox)] as follows:
 - 5.1.2.1 rV-PANVAC™ 2 x 10⁸ pfu SQ at week 0 (+/- 7 days) only.
 - 5.1.2.2 rF-PANVAC™ 1 x 10⁹ pfu SQ at weeks (+/- 7 days) 3, 7, 11, and 15.
- 5.1.3 All subjects will provide blood, urine, and tissue (if available) at study entry and at the end of the study. Tissue at study entry can be obtained either from outside FFPE or from previous TURBT performed at NIH (see section 3.4.4.1). This tissue is required for diagnosis. All subjects will also have blood drawn at weeks 3 and 8 to coincide with the start and end of BCG treatment. Urine samples will also be obtained before and after the 1st and 3rd instillation of BCG as defined in Section 10.1.2.
- 5.1.4 All subjects will undergo tuberculin skin testing using purified protein derivative (PPD) at study entry (prior to receiving BCG instillation #1) and around the time of the week 17-20 cystoscopy/EUA. The associated skin reaction will be evaluated by a health care provider within 48-72 hours after injection. Skin induration greater than 10mm in diameter will be considered a positive result. Initial PPD results do NOT preclude subsequent treatment with BCG – these results will only be used to assess the immunologic response to BCG (see section 10.1.1).

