5.8 CRITERIA FOR REMOVAL FROM PROTOCOL THERAPY AND OFF STUDY CRITERIA

Prior to removal from study, effort must be made to have all subjects complete a safety visit approximately 30 days following the last dose of study therapy.

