14.2 SECONDARY ENDPOINTS

Using Kaplan-Meier methods, we will estimate the probability distribution of progression-free survival and the time to recurrence. Results will be summarized by point estimates (12 months) with 95% CI. Exploratory analyses of these secondary objectives will compare the two treatment arms using the log rank test. Fisher's exact test will be used to compare frequency distributions of toxicity grades between the two arms.

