14.4 REPORTING AND EXCLUSIONS

14.4.1 Evaluation of Toxicity

All patients will be evaluable for toxicity from the time of their first treatment with rV-PANVACTM and rF-PANVACTM.

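### The toxicity comparison appears to set about 19 weeks of adverse-event follow-up on PANVAC against about 9 on BCG, with no common window, and sections 12.1.1.1 and 14.4.1 disagree on when evaluability starts

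*Combined protocol and SAP*

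**What the plan says.** - **End of collection.** Section 13.1: "Patients will be followed for adverse events for 30 days after removal from study treatment or until off-study, whichever comes first". Section 5.8 asks that subjects "complete a safety visit approximately 30 days following the last dose of study therapy".
- **Dosing.** Under section 5.1 the combination arm receives the vaccinia prime "pfu SQ at week 0 (+/- 7 days) only" and the fowlpox boosts "pfu SQ at weeks (+/- 7 days) 3, 7, 11, and 15". Both arms receive six weekly BCG instillations in weeks 3 to 8.
- **Start of evaluability.** Section 12.1.1.1: "All patients who receive at least one dose of protocol therapy will be evaluable for toxicity", counted from the first TICE BCG or rV-PANVAC dose. Section 14.4.1: "All patients will be evaluable for toxicity from the time of their first treatment with" rV-PANVAC and rF-PANVAC; BCG is not named.
- **Summary and test.** Sections 5.4 and 12.1.1.1 tabulate the highest grade per patient. Under section 14.2, Fisher's exact test "will be used to compare frequency distributions of toxicity grades between the two arms". No significance level, common window or exposure adjustment is given.
- **Visits (section 11).** The only required CBC, chemistry and PT/PTT after baseline are at weeks 17-20 in both arms, together with the biopsy. The BCG calendar has a history and physical at each of weeks 3 to 8, then at weeks 15 and 17-20. The PANVAC calendar adds week 11.

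**The concern.** A highest grade per patient can only rise as observation lengthens. If one arm is watched for roughly twice as long, its grade distribution moves upward even where the event rate per week is the same, and a test on patient counts cannot separate that from a treatment effect.

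The week 17-20 assessment sharpens this. Both arms have the same anaesthetic, cystoscopy, biopsy or resection and blood tests, yet these fall mostly inside the PANVAC window and wholly outside the BCG window. Haematuria or infection after the procedure, or a laboratory abnormality found that day, could count in one arm only.

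At stake is the prediction in section 2 that the combination shows no more treatment-related toxicity than BCG alone, and the comparative part of the evidence for secondary objective 1.2.2. The plan does align the time origin elsewhere: section 12.1.1.2 measures all durations from week 3 so that secondary outcomes can be compared between arms. Toxicity has no matching rule.

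**Working it through.** The plan states no window length and no level or power for the toxicity test, so it offers no figure of its own to reproduce on this point. Its one numerical safety input, the 6% anticipated serious adverse event rate in section 14.1, belongs to a stopping rule that does reproduce: exact stopping probabilities at 26 patients are 0.035 at 6% and 0.939 at 30%, against the stated 0.04 and 0.94.

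**1. Windows, with the 30 days counted from last dose (section 5.8).** Length = last dose week + 30/7 − first dose week.
- PANVAC: 15 + 4.3 − 0 = 19.3 weeks, ending at week 19.3. Moving the last dose by its 7-day tolerance gives 18.3 to 20.3.
- BCG: 8 + 4.3 − 3 = 9.3 weeks, ending at week 12.3.
- Ratio: 19.29/9.29 = 2.08. Counting both arms from week 3 gives 16.3 against 9.3 weeks, ratio 1.75.
- A patient taken off study for recurrence at the week 17-20 biopsy (sections 5.1.6 and 5.2.2.3) leaves the window then. At week 17 that is 17.0/9.29 = 1.83.

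**2. Windows, if removal means the end of the 20-week course.** Both end at 20 + 4.3 = 24.3. Lengths are 24.3 and 24.3 − 3 = 21.3 weeks, ratio 1.14.

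**3. Effect on frequencies when PANVAC adds no toxicity.** Let p be the control frequency, H = −ln(1 − p), and f the share of H from BCG-related events that both windows capture. The PANVAC arm then shows 1 − exp{−H[f + (1 − f) × 2.08]}. The value of f is an assumption; f = 0 is a constant weekly rate throughout.

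| Control frequency | f = 0 | f = 0.5 | f = 0.75 |
|---|---|---|---|
| 10% | 19.7% | 15.0% | 12.5% |
| 20% | 37.1% | 29.1% | 24.7% |
| 30% | 52.3% | 42.2% | 36.4% |

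Procedural events at weeks 17-20 are not modelled. Under the reading in step 2, even with f = 0, control frequencies of 10, 20 and 30% would show as only about 11, 22 and 33%.

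**4. Effect on Fisher's test.** Exact enumeration, 24 controls and 25 PANVAC patients, two-sided 5% (assumed, since no level is stated), f = 0, no true difference in weekly rate:

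| Control frequency | Equal windows | 19.3 vs 9.3 weeks |
|---|---|---|
| 6% | 0.4% | 2.6% |
| 20% | 3.2% | 18.6% |
| 40% | 4.0% | 41.7% |

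Almost all of the added rejections go against PANVAC. The 6% row uses the plan's rate for serious events; the test in section 14.2 covers toxicity grades generally, where frequencies can be higher.

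**5. The two evaluability rules.** Section 12.1.1.1 gives every treated patient a start date: week 0 for PANVAC, week 3 for BCG. Taken literally, section 14.4.1 gives a BCG-only patient none, because that patient never receives either vaccine. The two cannot both define the start.

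**The case against.** **The end date is inferred.** Section 13.1 counts from removal, the criteria in section 5.8.1 do not include completing therapy, and sections 5.1.6 and 5.7 speak of a 20-week course for all subjects. This stands as a limit on certainty. Section 5.8 favours the last-dose reading without settling it, and the missing definition itself needs repair.

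**Much BCG toxicity is captured equally.** Section 8.1.2.1 describes irritative symptoms starting 4-6 hours after instillation and lasting 24-72 hours. Both windows cover weeks 3-8 and the following 30 days. Attribution is recorded (section 8.2.1.1), the section 2 hypothesis concerns treatment-related events, and much of the extra PANVAC time is genuine vaccine exposure. This also stands: it makes f = 0 an upper illustration. It does not remove the tilt, because the tabulation is not limited to related events and unrelated or procedural events remain unevenly counted.

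**Stronger readings that the documents do not support.** A reader might infer that section 14.4.1 makes the control arm non-evaluable. It does not: its subject is all patients, and section 12.1.1.1 names TICE BCG and reports each arm. A reader might infer that the safety objective cannot be answered. Objective 1.2.2 is not worded as a comparison, and the pause after six patients, the stopping rule and the per-arm tables address it within the combination arm. A reader might infer that a false excess is bound to appear. It is not: that depends on how many events fall outside weeks 3-12 and are unrelated to vaccine.

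**Conclusion.** The point holds as a tilt against PANVAC in a secondary safety comparison, together with a contradiction between two definitions. On the last-dose reading the windows are 19.3 and 9.3 weeks, ratio 2.08. If removal means the end of the 20-week course, the ratio falls to 1.14 and the problem is small.

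The direction is clear on the first reading; the size is not. A control frequency of 20% could show as 25 to 37%, depending on how far events cluster around BCG, before any procedural events. The upper end assumes one constant weekly rate, which fits BCG toxicity poorly. At a 6% event rate the test itself is little affected (2.6% rejection), and the distortion lies mainly in the estimated frequencies. Sections 12.1.1.1 and 14.4.1 conflict whichever reading of the window is right.

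**What to change.** 1. **One evaluability rule.** Reconcile section 14.4.1 with section 12.1.1.1, so that toxicity is evaluable from the first dose of any protocol therapy in either arm.
2. **A stated end date and a common comparison window.** Say in section 13.1 what event starts the 30 days. Make the section 14.2 comparison over the same calendar weeks in both arms, for example from week 3 (the origin in section 12.1.1.2) through the week 17-20 visit that controls already attend. Show biopsy-related events separately.
3. **Keep the full summary.** Report each arm to 30 days after last dose as descriptive, so that reactions to the week 0 prime and to late or delayed vaccine doses are not cut off.

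Section 8 records that the study closed with CTEP on 5/1/2019, so collection may already be complete. In that case, compare dated events over the weeks both windows cover, about 3 to 12, or give exposure-adjusted rates beside Fisher's test. The shared-weeks comparison is narrower, since it leaves out the week 0 prime and the week 15 boost.

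**Cost.** Wording changes in sections 12.1.1.1, 13.1, 14.2 and 14.4.1, and about 8 more weeks of recording in controls (20 − 12.3 = 7.7), at visits mostly already scheduled (weeks 15 and 17-20). Starting the common window at week 0 instead would keep the prime in the comparison, but would add 3 further weeks in controls and require the comparison to count from randomisation rather than first dose.
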